9.4.4 SAFETY ANALYSES

We will track and document safety events related to the device during the clinical trial.

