6 STUDY INTERVENTION

6.1 STUDY INTERVENTION(S) ADMINISTRATION

6.1.1 STUDY INTERVENTION DESCRIPTION

The Teva Digihaler™ System consists of 4 devices. Device 1 is the ProAir® Digihaler™, which is the test IMP. The 3 investigational medical devices are: Device 2 - Patient-facing App; Device 3 - DHP (cloud solution); and Device 4 - Provider-facing dashboard. Patients will receive 2 ProAir® Digihaler™ devices at the face-to-face visits and can request additional devices if these devices have been completely used. A three-month supply of maintenance AirDuo® Digihaler™ will be provided at each in person visit and only after verification that data from the previous device has been downloaded. Patients will receive instructions for using the ProAir® Digihaler™ and AirDuo® Digihaler™ from the investigational center personnel. Patients will be instructed to return all inhalers to the investigational center at the end of treatment visit or at early termination. These devices will be brought to the in-person visits and the data download will be confirmed, after which the devices will be discarded.

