7.2 PARTICIPANT DISCONTINUATION/WITHDRAWAL FROM THE STUDY

1. Patient withdraws consent or withdrawal from the study for any reason
2. Patient experiences an adverse event or other medical condition which indicates to the investigator that continued participation is not in the best interest of the patient.
3. Patient develops an illness that would interfere with his/her continued participation.
4. Patient is noncompliant with the study procedures and assessments in the opinion of the investigator.

Patients should be treated with standard of care after withdrawal from or termination of the study as appropriate. We will obtain information on patients in the case of withdrawal from the study or discontinuation from IMP. Results of any evaluations and observations, together with a narrative describing the reason(s) for withdrawal from the study or discontinuation from IMP, must be recorded in the source documents. The case report form (CRF) must document the primary reason for withdrawal from the study or discontinuation from IMP.

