8.1.1.2 IN PERSON/CLINICAL VISITS (V3, V6, V9, V12)

Patients will return to clinic every three months to check in with the study team and to provide additional inhalers for the study. During the in-person visits the following events will take place:

- Review of Current Medications
- Review of Asthma Exacerbations and Healthcare Utilization
- Collection of Clinical Variables (*if available*) including FeNO, CBC w. Differential, and Immunoglobulin E (IgE) Levels
- Dispensation of Inhaler
- Adverse Event Assessment
- Collection of Patient Reported Outcomes

- Asthma Control Test (ACT), AIR-Q, SGRQ
- Device Re-Education (As Needed)

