8.2 SAFETY AND OTHER ASSESSMENTS

In this study, safety will be assessed by qualified study personnel by evaluating reported adverse events, device safety (as assessed by adverse device effects and serious adverse device effects), and use of concomitant medications.

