8.3 ADVERSE EVENTS AND SERIOUS ADVERSE EVENTS

8.3.1 DEFINITION OF ADVERSE EVENTS (AE)

Safety Considerations: The external sponsor/collaborator shall have the sole responsibility for the collection and recording of all reported Adverse Events (AEs), Serious Adverse Events (SAEs), Pregnancies, Adverse Device Effects and Serious Adverse Device Effects throughout the entire study. In keeping with good clinical practice or good pharmacovigilance practice, and 21 C.F.R. Part 314 as the case may be, the external sponsor/collaborator will be required to report and notify the FDA, Institutional Review Boards (IRBs), Teva Pharmaceuticals (Teva), and any other collaborators/investigators of all situations mentioned below, within twenty-four (24) hours from receiving information of the situation. The event will be reported to Teva by submitting the collected information to the Teva Local Safety Officer.

- (a) All related Serious Adverse Events
- (b) All Serious Adverse Device Effects.
- (c) Any medical event which may reasonably be believed to impair the integrity, validity or ongoing viability of the Study

Pharmacovigilance approved definitions of AEs and SAEs and reporting and recording procedures will be followed as noted below.

In this study, safety will be assessed by qualified study personnel by evaluating reported adverse events and device safety (as assessed by adverse device effects and serious adverse device effects). The external sponsor/collaborator will be responsible for the collection and recording of all reported Adverse Events (AEs), Serious Adverse Events (SAEs) Pregnancies, Adverse Device Effects and Serious Adverse Device Effects throughout the entire study.

Definitions:

Adverse Event

An adverse event (AE) is any untoward medical occurrence, unintended disease or injury, or untoward clinical signs (including abnormal laboratory findings) in patients or clinical investigation subjects, users or other persons, whether or not related (causal relationship) to the pharmaceutical product (treatment), investigational medical device, or comparator. This definition includes events related to the procedures involved. For users or other persons, this definition is restricted to events related to investigational medical devices.

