An adverse event can, therefore, be any unfavorable and unintended physical sign, symptom, or laboratory parameter that develops or worsens in severity during the course of this study, or significant worsening of the disease under study or of any concurrent disease. A new condition or the worsening of a pre-existing condition will be considered an adverse event. Stable chronic conditions (such as arthritis) that are present before study entry and do not worsen during this study will not be considered adverse events.

Accordingly, an adverse event can include any of the following:

- intercurrent illnesses
- physical injuries
- events possibly related to concomitant medication
- significant worsening (change in nature, severity, or frequency) of the disease under study or other pre-existing conditions
- drug/drug or drug/device or device/device interactions
- events occurring during diagnostic procedures of this study

Worsening of asthma that occurs during the study that is not typical of the patient's daily symptoms or leads to the patient's discontinuation will be considered an adverse event.

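### Section 9.4.4 limits the safety analysis to device-related events, so no summary of all adverse events is planned although all are collected

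*Combined protocol and SAP*

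**What the plan says.** Section 9.4.4 (Safety Analyses) is one sentence: "We will track and document safety events related to the device during the clinical trial". It names no analysis set, denominator, coding, table, or breakdown by seriousness or relatedness.

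The sections on safety data are broader. Section 8.2 says that safety will be assessed "by evaluating reported adverse events, device safety (as assessed by adverse device effects and serious adverse device effects), and use of concomitant medications". Section 8.3.1 defines an AE as an untoward occurrence "whether or not related (causal relationship) to the pharmaceutical product (treatment), investigational medical device, or comparator". It then adds a rule for the disease itself: "Worsening of asthma that occurs during the study that is not typical of the patient's daily symptoms", or that makes the patient discontinue, is an AE. The schedule in Section 1.3 marks AEs at baseline, at Visits 1 to 12 and at follow-up. The clinic-visit list in 8.1.1.2 includes "Adverse Event Assessment", and the phone list in 8.1.1.3 has the same item.

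On products, Section 6.1.1 lists four devices. It states: "Device 1 is the ProAir® Digihaler™, which is the test IMP"; the other three are the app, the cloud platform and the dashboard. AirDuo Digihaler is not on that list, although the same section supplies it and the synopsis makes it part of the study intervention. Section 7.2 adds: "The case report form (CRF) must document the primary reason for withdrawal from the study or discontinuation from IMP".

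**The concern.** The plan collects one set of safety data and analyses a smaller one. Whether an AE enters the analysis depends on its being judged device-related. That judgement is made open label, in a disease whose symptoms overlap with the events of interest. Asthma worsening is easily put down to the asthma, and a drug effect of an inhaled product need not be called a device event. If 9.4.4 is followed as written, the study could report that no device safety problem was seen without ever reporting how many AEs or serious AEs occurred.

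The study also provides for patients to change their maintenance inhaler to AirDuo Digihaler (5.1, criterion 5) and to change back if they find an inhaler ineffective (6.4). A reader of the results would want to know how often patients changed back and why. Section 9 plans no such count.

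**Working it through.** The documents give no safety figure to reproduce. The check sets sections side by side, with a short calculation of what a full table could show.

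**1. Scope.**
- Assessed (8.2): all reported AEs, device effects, concomitant medication.
- Defined as AEs (8.3.1): related or not, for drug or device, including atypical asthma worsening.
- Analysed (9.4.4): events related to the device.

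AEs in the first two and not in the third have no planned output under 9.4.4.

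**2. Does another section fill the gap?**
- 9.3 defines its population by biologic treatment, not by receipt of a study inhaler, so there is no safety set.
- 9.4.5 summarises inhaler, spirometry, clinical, demographic, asthma-outcome and radiographic variables. AEs are not listed.
- 9.4.8 plans no tabulation of individual data except for illustration, so AE listings are not planned either.
- 9.4.9 is an open-ended exploratory list that does not mention AEs.

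None of them plans an AE summary.

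**3. Asthma worsening.** An exacerbation under 8.1.2.3 needs a burst of systemic steroids, an emergency or urgent care visit requiring steroids, or hospitalization. The exploratory objective words this differently and adds a doubling of maintenance steroids. The AE rule in 8.3.1 requires none of these. Worsening that meets the AE rule only is not counted as an exacerbation. It can reach the analysis indirectly, through the Asthma Control Test (ACT) or spirometry, but not as an AE.

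**4. Contacts.** Baseline + 12 visits + follow-up = 14 per patient. For the 100 patients assumed in 9.2, 14 × 100 = 1,400 scheduled contacts, of which 13 × 100 = 1,300 follow the first dispensing. These are opportunities to record an AE, assuming no dropout. They do not measure how many AEs occur or go unsummarised.

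**5. What a full table could show at n = 100.**
- Chance of seeing an event of true rate p at least once, 1 − (1 − p)^100: p = 1%, 0.63; 2%, 0.87; 3%, 0.95; 5%, 0.99.
- Upper limit with 0/100 events: one-sided 95%, 1 − 0.05^(1/100) = 3.0%; two-sided, 1 − 0.025^(1/100) = 3.6%.
- With 10/100 events, the exact (Clopper-Pearson) 95% interval is 4.9% to 17.6%.

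**6. Status of AirDuo Digihaler.**
- 6.1.1: not among the four devices and not the named IMP, though its resupply rule refers to the previous device.
- 6.1.2: the high-dose AirDuo product is called a device.
- 6.2.1 and 6.2.2: all inhalers are returned and reconciled under IMP accountability, and the AirDuo dose is described in the IMP formulation and labelling section.
- 7.1: both inhalers are called digihaler devices.
- Synopsis: part of the study intervention.

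These do not agree, so it is unclear whether the device in 9.4.4 includes AirDuo. Separately, 4.3 says that no therapy changes were warranted, while 5.1 asks for willingness to switch to AirDuo and/or use ProAir Digihaler.

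**The case against.** The strongest reply is that little is lost. Exacerbations, hospitalizations, emergency visits and ACT scores are endpoints, and FEV1 change is a secondary endpoint. Asthma outcomes are summarised in 9.4.5 and tested by adherence group in 9.4.3, where exacerbations are also the modelled outcome. Section 10.1.6 has safety events logged and reviewed monthly by the principal investigator and with the sponsor, with no device restriction. Related serious AEs and all serious device effects are reported within 24 hours (8.3.1, 8.3.4). A change of inhaler leaves a trace in the concomitant-medication record (6.5.1) and, for non-digital inhalers, the diary (6.4). The products are approved, the study is described as minimal risk (2.3.3), and it does not evaluate drug efficacy (8.1).

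All of this stands, and it rules out several stronger readings:

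- A reader might infer that asthma worsening is not analysed. It is, as an asthma outcome. What is missing is its summary as an AE.
- A reader might infer that AirDuo events fall outside the safety analysis because only ProAir Digihaler is the named IMP. The AE definition is not tied to the named IMP, and 6.1.2 and 7.1 call AirDuo a device. The documents show inconsistency, not exclusion.
- A reader might infer that AEs after a switch go unreported. Logging, monthly review and expedited reporting contradict that.
- A reader might take the switch to be universal. The criterion says and/or.

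The reply does not show a planned summary of all AEs. A log review is oversight, and the efficacy-type outcomes cover only part of what 8.3.1 calls an AE.

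**Conclusion.** The point holds as a gap in the analysis plan. Section 9.4.4 is narrower than 8.2 and 8.3, and nothing else in Section 9 makes up the difference. Following the plan as written gives a safety output filtered by an open-label relatedness judgement.

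The size cannot be stated as a number of events, because the documents give no expected AE rate or device-related share. The calculations above assume 100 patients with complete follow-up and serve only to show that a full table is worth having. The conclusion rests on reading 9.4.4 literally and on no AE summary being specified in a document outside this one.

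The inconsistent status of AirDuo is secondary. It affects how relatedness and the discontinuation record in 7.2 would be applied, but it does not cause the gap. This is an inexpensive correction that should be made before analysis; it is not a threat to the primary objective.

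**What to change.** Rewrite 9.4.4 to:

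- define a safety set of all patients dispensed at least one study inhaler;
- tabulate all AEs, serious AEs, adverse device effects and serious adverse device effects in that set, with asthma-worsening AEs shown separately;
- give each table overall and by relationship to ProAir Digihaler, AirDuo Digihaler and the app, cloud and dashboard;
- count switch-backs from either inhaler, with reasons where recorded. This also allows the 10% limit on switching in 6.4 to be checked (10 of 100 patients).

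Any listing by time since the AirDuo switch should be descriptive only. It has no control, and it is confounded with biologic initiation because patients may start a biologic after enrolment (5.1, criterion 3).

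Reconcile the status of AirDuo Digihaler across the synopsis, 6.1.1, 6.1.2, 6.2 and 7.1, and reconcile 4.3 with 5.1.

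The cost is wording and a few more tables from data already collected, with no new study procedure. One assumption needs checking: the documents do not show whether the AE form records relatedness separately for each product. If it does not, the by-product breakdown needs one more field.

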9.4.5 BASELINE DESCRIPTIVE STATISTICS

Count, mean, standard deviation, median, IQR will be computed for continuous variables and percentages for categorical variables – daily, time-of-day, and per-inhalation parameters, exhalation spirometer variables, clinical and demographic variables, asthma outcomes, radiographic variables. Summaries will be computed for males vs. females, adherence group, and response group.

9.4.6 PLANNED INTERIM ANALYSES

We will perform the initial analysis once 50% of the study population has completed six months of follow-up within the study.

9.4.7 SUB-GROUP ANALYSES

See secondary endpoints #3 (adherence groups) and #4 (responder groups).

9.4.8 TABULATION OF INDIVIDUAL PARTICIPANT DATA

We do not plan to tabulate or report individual participant data, except in the case where we determine that one or more participant's data would be useful for explaining a general concept or idea, or is representative of an overall trend, and as such may be displayed (without any identifying information) in a data graphic or visualization with or without an accompanying data table.

9.4.9 EXPLORATORY ANALYSES

We plan to conduct extensive exploratory analyses including but not limited to: data cleaning and aggregation, outlier analysis, multicollinearity (correlation) analysis, sex effect analysis, age effect analysis, time series analysis, unsupervised cluster analysis, univariate testing (T-tests, Fisher's Exact Test, Wilcoxon Test, Chi-Squared Test, Tukey's Honest Significant Difference (HSD) Test), multivariable linear and non-linear regression, feature creation and selection for machine learning models, feature scaling and centering, training machine learning models using repeated k-fold cross-validation, and extensive data visualization for correlations and time series analysis.

10 SUPPORTING DOCUMENTATION AND OPERATIONAL CONSIDERATIONS

10.1 REGULATORY, ETHICAL, AND STUDY OVERSIGHT CONSIDERATIONS

10.1.1 INFORMED CONSENT PROCESS

It is the responsibility of the named investigator to assure that all study subjects undergo an appropriate process of written informed consent that has been reviewed and approved by their local Institutional Review Board. The investigators will inform all subjects as to the nature, aims, duration, potential hazards, and procedures to be performed during the study and that his/her medical records and study-related documents may be reviewed by the FDA or sponsoring companies in a manner designed to protect their confidentiality. This protocol must receive approval by the Institutional Review Board at each participating site prior to implementation of the study at that site. Investigators must also disclose to subjects any existing conflicts of interest and explain that patients are completely free to refuse to enter the study or to withdraw from it at any time without prejudice to their medical care.

10.1.1.1 CONSENT/ASSENT AND OTHER INFORMATIONAL DOCUMENTS PROVIDED TO PARTICIPANTS

Consent will be copied and provided to the patient after it has been signed. The documentation will then be scanned into the EMR per University of Michigan protocol.

10.1.1.2 CONSENT PROCEDURES AND DOCUMENTATION

The protocol will be discussed in detail with all potentially eligible patients and the essential components of the informed consent process personally confirmed by a responsible investigator before the consent is signed and countersigned. The subject will sign the informed consent document prior to any procedures being done specifically for the study. All revisions of the protocol must be reviewed by the IRB and reflected in the consent form. Patients will receive copies of all consent documents and HIPAA forms for their records and these documents will detail emergency contact numbers for the study and independent reporting numbers for the local IRB in the event that they have any concerns or questions about the process of consent or the handling of human subjects.

10.1.2 STUDY DISCONTINUATION AND CLOSURE

The investigators and/or sponsor reserve the right to terminate the study at any time. If this becomes necessary, appropriate procedures for continuing long-term follow-up and assuring the adequate treatment and safety of the participating subjects will be arranged after review and approval by the study sponsor, Institutional Review Boards and the FDA.

10.1.3 CONFIDENTIALITY AND PRIVACY

Every participating clinical site will maintain appropriate medical and research records for this trial, in compliance with ICH E6 and regulatory and institutional requirements for the protection of confidentiality of subjects. Participating clinical sites will also obtain institutional authorization for external monitoring by the Sponsor, Data Coordinating Center and the FDA to examine (and when

permitted by applicable law, to copy) clinical records for the purposes of quality assurance reviews, audits, and evaluation of the study safety, progress, and data validity.

10.1.4 FUTURE USE OF STORED SPECIMENS AND DATA

Source data are defined as all information, original records of clinical findings, observations, or other activities in a clinical trial necessary for the reconstruction and evaluation of the trial. Examples of these original documents and data records include, but are not limited to, hospital records, clinical and office charts, laboratory notes, memoranda, subject’s memory aids or evaluation checklists, pharmacy dispensing records, recorded audio tapes, recorded data from automated instruments, copies or transcriptions certified after verification as being accurate and complete, microfiches, photographic negatives, microfilm x-rays, and subject files and records kept at the pharmacy, at the laboratories, and medico-technical departments involved in the clinical trial. It is acceptable to use CRFs as source documents when the data is collected and recorded there as the primary source of information, but CRFs will not constitute the only form of source document information for this trial.

10.1.6 SAFETY OVERSIGHT

DSMB will not be required for this study. Safety events will be tracked in a log and reviewed by the principle investigator on a monthly basis. These safety events will also be reviewed with the sponsor during monthly calls.

10.1.7 CLINICAL MONITORING

No clinical monitoring will be required for this study. Oversight for the accuracy of data entry will be the responsibility of the Clinical Research Project Manager that will be overseeing the coordinator working on this study.

The clinical research project manager will ensure that:

- Data collected and entered into the database are verifiable against source documents for the subjects.
- Appropriate consent is obtained for each subject prior to study procedures.
- The rights and well-being of subjects are being protected.

- The study is conducted in accordance with the currently approved protocol (including study treatment being used in accordance with the protocol), with any other study agreements, with GCP and with applicable regulatory requirements.
- Will work with the research pharmacy on drug accountability and will review logs on a bimonthly basis.

10.1.8 QUALITY ASSURANCE AND QUALITY CONTROL

The clinical trial site has established a set of standard operating procedures (SOPs) governing the processes used to ensure patient privacy and data confidentiality, including the use of anonymous subject IDs on CRFs and in reports. Redcap® enables compliance with Good Clinical Practice (GCP) and regulatory requirements by providing differentiated user roles and privileges, password and user authentication security, electronic signatures, SSL encryption, and comprehensive auditing to record and monitor access and data changes.

10.1.9 DATA HANDLING AND RECORD KEEPING

10.1.9.1 DATA COLLECTION AND MANAGEMENT RESPONSIBILITIES

Data collection is the responsibility of the clinical trial staff at the site under the supervision of the site PI. The investigator is responsible for ensuring the accuracy, completeness, legibility, and timeliness of the data reported. In addition to the protocol, the DCC will prepare a Manual of Operations will provides additional detail on data collection procedures, including source documentation, eCRF completion guidelines, data handling procedures and procedures for data monitoring and quality control that ensure these data are accurate, consistent, complete and reliable and in accordance with ICH 36.

